We hypothesize that genes implicated in fear extinction will provide general prediction of the success of exposure treatment, and that the degree of additional benefit associated with DCS will be influenced by NMDA-related glutamatergic loci.

3. Subject Selection

Inclusion criteria are a diagnosis of BDD by DSM-IV standards and a BDD Yale-Brown Obsessive Compulsive Scale score greater than or equal to 24 in people 18 years of age or older. Subjects must be able to give informed consent, and females of childbearing potential must have a negative urinary beta-HCG test. Pregnant or breastfeeding women, people taking medications that may interfere with DCS, and people with a history of seizure disorder or other serious medical illnesses such as cardiovascular, hepatic, renal, respiratory, endocrine, neurological or hematological disease are excluded from this study. Other criteria for exclusion are comorbid

psychiatric diagnoses (alcohol dependence, bipolar disorder, psychosis, borderline personality disorder, organic mental disorder, or developmental disorder). Also excluded are patients taking medications that may lower the seizure threshold, including clozapine, pethidine, and the following antibiotics in high dosages: penicillins, cephalosporins, amphotericin, and imipenem. Those deemed to pose a serious suicidal or homicidal threat will be excluded. If patients have any other comorbid disorder, the BDD symptoms must be the primary concern. Furthermore, current psychotherapy and failure to benefit from ten or more sessions of previous CBT treatment are a rule-out. Moreover, if a patient is taking a psychotropic medication, he or she must be at a stable dose prior to enrolling in the study.

Participants will be withdrawn from the study if their clinical condition deteriorates substantially, as defined by a rating of 6 (much worse) or 7 (very much worse) on the Clinical Global Impressions-Improvement (CGI-I) scale. Participants may also be withdrawn if, in the judgment of the PI or therapist, remaining in the study poses a substantial risk to the participant, or if a higher level of care is needed.

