Primary analyses: Our primary hypothesis is that ERP in combination with DCS is more effective than ERP in combination with a placebo. To measure this, the BDD-YBOCS will be the primary outcome measure. The main analyses will compare the two patient groups at mid-treatment and post-treatment using analysis of variance (ANOVA) and analysis of covariance (ANCOVA, controlling for BDD-YBOCS-pretreatment scores). To further determine the clinical significance of these findings, we will use the Jacobson and Truax (1991) formula to calculate the percentage of patients who fulfill the criteria for reliable and clinically significant change in each treatment condition at mid-treatment and post-treatment. Fisher's exact test for differences in frequencies of responders between the two patient groups will be performed. We will further compare the two groups at the 1- and 6-month follow-up assessments.

Power analysis: A power analysis with a sample size of 25 per group and $p < .05$ reveals that this study will convey 80% power to detect a group difference in post-treatment BDD-YBOCS scores of $d = 0.78$, which is a large effect size. Moreover, we will estimate between-group effect sizes of this pilot study to be used in designing future studies.

Secondary analyses: We hypothesize that patients who receive DCS augmentation will have greater improvement on the CGI-I, BDI, BDD-SS, and Disability Inventory at mid-treatment, post-treatment and 1- and 6-month follow-up assessments than patients who receive the placebo. ANCOVAs (controlling for pretreatment scores) and multivariate ANCOVAs (MANCOVAs) will be used for these analyses as described above, and effect sizes will be computed. Furthermore, the Cognitive and Behavioral Change Measures will be used to identify in more detail within which session, or between which sessions, any changes occurred.

Predictors of outcome: We also wish to evaluate whether ERP in combination with DCS is particularly effective or ineffective for different symptoms (as measured by the BDD Symptom Scale), attitudes (i.e., patient's judgments about the credibility of the treatment, as measured by the Expectancy Rating), or comorbid problems (e.g., depression). These factors will be included in regression analyses. We also intend to explore the relationship between minority status and treatment outcome; however, power will be limited given the small sample size.

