Mechanisms of improvement: We are also interested in potential mechanisms of change during treatment. These can be tested with multiple regression procedures via hierarchical regression models. Treatment group (DCS vs. placebo) will be the independent variable, changes in BDD symptom severity (BDD-YBOCS) the dependent variable, and, for example,

changes in beliefs as measured by the Schema Questionnaire will be the mediator. We will follow the procedures for establishing statistical mediation outlined by Baron and Kenney (1986), using residual gain scores as the measure of change in both the dependent variable and the mediator (Cohen, 1983). These residual scores will give a reliable estimate of changes in symptom severity and beliefs independent of differences in baseline severity. We will interpret our results with caution because the absence of statistical significance may reflect the somewhat limited power with only 50 patients.

Genetic Analyses: We will use quantitative trait association analytic methods to examine whether alleles and/or haplotypes of the loci selected for analyses are associated with outcome of ERP with or without DCS. Analyses will be conducted in two stages. The initial analyses will examine whether any of the genetic variants are associated with ERP outcome indexed by change in BDD-YBOCS score from baseline (at end of treatment and at 1-month and 6 month follow-up). The analyses will include a main effect analysis of each genetic variant as well as a gene x treatment interaction analysis, to examine whether allelic effects on outcome differ by treatment condition (DCS vs. placebo). If evidence of interaction is detected, we will also examine allelic effects within treatment group. For example, we expect that genes involved in NMDA receptor function (e.g. the *GRIN1* gene whose product includes the glycine (DCS) binding domain) may mediate response to DCS.

In the second stage, genetic predictors demonstrating univariate association will be entered into a multivariable linear regression model along with other predictors of treatment response in an effort to build a model that parsimoniously explains the greatest proportion of variance in response to ERP (with and without DCS). For genes in which more than one polymorphism shows evidence of association, we will select the SNP with the minimum p value to enter into the multivariable model.

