Univariate single marker and haplotype-based analyses will be conducted using WHAP (Curran et al., 2005; <http://www.broad.mit.edu/~shaun/whap/>). Using an approach similar to those of Schaid et al. (2002) and Zaykin et al. (2002), WHAP is based on a two-stage method. The primary test is a regression-based analysis of association between marker (or haplotype) and trait, with one regression coefficient per marker (or haplotype). The independent secondary test analyses the relationship between marker (or haplotype) similarity and regression coefficient similarity. Evidence from the primary and secondary stages can be combined to provide a more powerful test of association, by combining log-transformed P values. The method is based on a mixture of regression models which accounts for the potential ambiguity in individuals' statistically-inferred haplotypes. For H haplotypes, a single omnibus test is performed to test jointly for any difference in haplotype effect, which is an H

– 1 single-degree-of-freedom test. The independent secondary test assesses whether pairs of more similar haplotypes show more similar effects. A multivariate weighted least squares regression of haplotype effect similarity on haplotype genetic similarity is used and empirical significance levels are determined by permutation testing. We will define haplotype blocks using the conservative definition of Gabriel et al. (2002) as implemented in Haploview (Barrett et al., 2004).

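### The stage 1 genetic analyses take change in BDD-YBOCS as outcome and name no baseline covariate; naming the pretreatment score would cost one degree of freedom and could gain precision

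*Combined protocol and SAP*

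**What the plan says.** All of the relevant text is in section 6, Biostatistical Analysis, except the entry criterion.

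- **Genetic Analyses, stage 1.** The outcome is "ERP outcome indexed by change in BDD-YBOCS score from baseline", taken "at end of treatment and at 1-month and 6 month follow-up". The tests are "a main effect analysis of each genetic variant as well as a gene x treatment interaction analysis". The later description of the software presents a regression of trait on marker or haplotype, with a single coefficient for each. No baseline covariate appears in either place.
- **Genetic Analyses, stage 2.** Variants that show univariate association are "entered into a multivariable linear regression model along with other predictors of treatment response". Those other predictors are not listed.
- **Primary analyses.** The arms are compared by ANOVA and also by ANCOVA, the latter "controlling for BDD-YBOCS-pretreatment scores". The secondary outcomes are likewise analysed by ANCOVA on pretreatment scores.
- **Mechanisms of improvement.** Mediation uses residual gain scores, on the stated ground that they do not depend on baseline severity.
- **Section 3, Subject Selection.** Entry requires a "BDD Yale-Brown Obsessive Compulsive Scale score greater than or equal to 24".

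**The concern.** The plan adjusts for baseline in its treatment comparison and its mediation analysis, and gives a reason in the latter that applies equally to genotype groups. The genetic analysis follows directly, uses change, and says nothing about adjustment or why it would differ.

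Two things are at stake. The first is precision: section 6 concedes limited power with 50 patients, and because genetics is optional, 50 is the most that the trial itself can contribute to these tests. The second is interpretation. Patients enter on a high score, so regression to the mean may tie change to the starting score. A genotype group that happens to start higher can then seem to respond better.

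**Working it through.** **The plan's own figure.** The plan states 80% power for d = 0.78 with 25 per group. The two-sided normal approximation gives 78.7% and the noncentral t gives 77.1%. The stated figure is reproduced to within about 2 points by the normal approximation and is not in dispute. The plan gives no power or sample size for the genetic analyses.

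**Inputs.** N = 50 and alpha 0.05 come from section 6 (two-sided is assumed). The baseline–post correlation rho and the two SDs are not in the protocol. I take rho = 0.3, 0.5, 0.7, and k = baseline SD / post SD = 1, 0.75, 0.5. Values of k below 1 represent narrowing of the baseline scores by the entry cut-off.

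**Residual variance.** Write s0 for baseline SD and s1 for post SD.

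- Change, unadjusted: s0² + s1² − 2·rho·s0·s1
- Adjusted for baseline: s1²·(1 − rho²)
- Difference: (s0 − rho·s1)², which is never negative
- Ratio adjusted/change: (1 − rho²) / (1 + k² − 2·k·rho)

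Example at k = 1, rho = 0.5: 0.75 / (2 − 1) = 0.75. At k = 0.75, rho = 0.3: 0.91 / (1 + 0.5625 − 0.45) = 0.91 / 1.1125 = 0.82.

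| k | rho 0.3 | rho 0.5 | rho 0.7 |
|---|---|---|---|
| 1 | 0.65 | 0.75 | 0.85 |
| 0.75 | 0.82 | 0.92 | 1.00 |
| 0.5 | 0.96 | 1.00 | 0.93 |

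**Power.** Fix the effect so that a 1-df test at N = 50 has 80% power when adjusted, multiply the noncentrality by the ratio above, and recompute from the noncentral F. Unadjusted power is:

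| k | rho 0.3 | rho 0.5 | rho 0.7 |
|---|---|---|---|
| 1 | 62% | 68% | 73% |
| 0.75 | 72% | 77% | 80% |
| 0.5 | 78% | 80% | 77% |

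**Share of a chance baseline gap that passes into change.** The slope of post on baseline is rho·s1/s0 = rho/k, so the share is 1 − rho/k. At rho = 0.5:

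- k = 1: 1 − 0.5 = one half
- k = 0.75: 1 − 0.667 = one third
- k = 0.5: 1 − 1 = none

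At rho = 0.7 and k = 0.5 it is 1 − 1.4 = −0.4, so the sign reverses.

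**Type I error.** Null simulations used n = 50, additive genotype with allele frequency 0.3 (assumed), arm in the model and 10,000 runs per setting. They tested the genotype main effect.

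- Over all runs, both methods rejected close to 5% (4.7–5.1%).
- The absolute genotype–baseline correlation exceeded 0.2 in about 16% of runs. Within those runs, with equal SDs and rho 0.3, 0.5, 0.7, unadjusted change rejected in 14.6%, 11.3% and 9.2%; the adjusted model rejected in 5.1%, 4.0% and 4.8%.
- With post SD 1.5 times baseline SD and rho 0.5 or 0.7, the conditional rates for change were 6.0% and 5.4%.

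**The case against.** **The text is silent rather than explicit.** Indexing the outcome by change defines the dependent variable, not the covariates. With baseline in the model, change and post-treatment score give the same genetic coefficients, so the sentence is compatible with an adjusted analysis. This stands: the point is that no baseline covariate is specified, not that one is excluded. Stage 2 may already include baseline among its unnamed predictors, but stage 1 decides which variants reach it.

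**The contrast with the primary analysis is incomplete.** That analysis also lists an unadjusted ANOVA. True, but an ANCOVA stands beside it; the genetic section names no adjusted counterpart.

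**The gain may be close to nil.** The entry cut-off invoked for regression to the mean is also a reason to expect a narrower baseline SD, and then the gain is small. This stands and limits the size of the point.

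**Genotype is not randomised.** The secondary aim includes the genetics of BDD itself, so a variant could affect baseline severity. Change and adjusted analyses then answer different questions about the main effect, and adjustment is not automatically unbiased. This also stands. It does not touch the gene x treatment test in the same way, because arm is randomised within genotype.

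**A stronger reading does not hold.** A reader might infer that unadjusted change raises the false-positive rate of the genetic tests, or that half of any baseline imbalance always becomes apparent response. Neither follows. Overall type I error stays near 5%, because chance imbalance is already part of the change-score standard error. The one-half figure needs rho = 0.5 and equal SDs.

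**Conclusion.** The concern holds as a gap in specification with a nearly free improvement available. Leaving baseline out can lose precision and, apart from one degree of freedom, cannot gain any. The loss ranges from substantial (change-score variance to be cut by 35% at rho 0.3 with equal SDs) to nothing (a post-on-baseline slope of 1). The protocol gives no SD or correlation with which to narrow that range. Misleading response is conditional on a baseline gap seen in the data and does not make the procedure invalid overall. The case is clearest for the gene x treatment test. The impact is minor, because the genetics component is optional, serves a secondary aim and sits within a pilot.

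**What to change.** 1. **Stage 1, gene x treatment.** Include pretreatment BDD-YBOCS and treatment arm as covariates, with genotype and genotype x treatment, at each time point. The plan describes the software as fitting one coefficient per marker or haplotype and does not say whether it takes covariates. If it does not, use residual gain scores as the trait, as the mediation analysis does.
2. **Stage 1, genotype main effects.** Use the same baseline and arm adjustment. Report beside it the genotype–baseline association and the unadjusted change result, and say that the two analyses answer different questions if a variant affects baseline severity.
3. **Stage 2.** Name baseline BDD-YBOCS among the predictors.

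The cost is a few lines in section 6, one degree of freedom per model, a check of what the software accepts, and a short extra table for the main effects. No new data are needed, since BDD-YBOCS is already collected at pretreatment.

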This trial also presents a unique opportunity to examine genetic and biological mediators of treatment response to extinction-based interventions. Accordingly, we have added an optional genetics component to this study for willing participants. Although genetic association studies have been plagued by concerns that reported associations may be spurious and difficult to replicate, a key strategy for minimizing the risk of Type I error is selecting candidate loci with the highest prior probability of association. Fortunately, compelling candidate loci with strong probability of involvement in NMDA-receptor mediated fear extinction are readily available due to the growing body of work on the molecular basis of this phenomenon. Specifically we will focus our analyses on genes that meet one or more of the following criteria: (a) encodes a subunit of NMDA receptors involved in fear conditioning/extinction, (b) involved in the action of DCS or d-serine co-activation of NMDA receptors, or (c) gene product shown to mediate fear extinction in preclinical models. Based on review of the literature, we selected loci that meet these criteria and have the strongest supportive evidence.

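### Stage 2 of the genetic response analysis selects and refits variants on the same 50 or fewer patients, so its in-sample R-squared is biased upward and nothing in the plan validates it

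*Combined protocol and SAP*

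**What the plan says.** Genetic prediction of treatment response is one half of the secondary aim in section 2, which also states hypotheses for it. The method is in section 6, Genetic Analyses, in two stages.

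- **Stage 1.** The plan makes a "main effect analysis of each genetic variant as well as a gene x treatment interaction analysis". The outcome is "change in BDD-YBOCS score from baseline (at end of treatment and at 1-month and 6 month follow-up").
- **Stage 2.** The plan says that "genetic predictors demonstrating univariate association will be entered into a multivariable linear regression model", together with other predictors, "in an effort to build a model that parsimoniously explains the greatest proportion of variance in response to ERP". Within a gene: "For genes in which more than one polymorphism shows evidence of association, we will select the SNP with the minimum p value".

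No entry threshold and no stage-2 time point are stated. No hold-out sample, cross-validation, shrinkage or replication is described for the stage-2 model.

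Two passages bear on false positives. Section 1 says that "a key strategy for minimizing the risk of Type I error is selecting candidate loci with the highest prior probability of association" and limits the work to eight named genes. Section 6 says of the secondary haplotype test that a "regression of haplotype effect similarity on haplotype genetic similarity is used and empirical significance levels are determined by permutation testing".

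On numbers, section 2 plans 50 treated patients. Section 1 says "we have added an optional genetics component to this study for willing participants". Under Evaluation of Population Structure, analyses may be confined to the largest ancestry subgroup.

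**The concern.** A variant enters stage 2 because it fitted these patients well, and it is then credited with how well it fits the same patients. Chance fit is counted as explained variance, and taking the smallest p within a gene adds to it. The share of variance explained is the quantity that stage 2 sets out to maximise, and it is the quantity that is biased.

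At stake is the credibility of the response half of the secondary aim. Even if no gene affects response, the procedure can return a genetic model whose R-squared looks meaningful.

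**Working it through.** **1. The plan's own figure.** The plan gives no sample size, power or R-squared for the genetic analysis. Its one design figure is 80% power for the primary comparison at d = 0.78 with 25 per group. The two-sided normal approximation gives Φ(0.78 × √(25/2) - 1.96) = Φ(0.798) = 78.7%, so the figure reproduces to within 2 points. It does not bear on this point.

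**2. Inputs.** From the documents: N at most 50 in two equal arms; eight core genes; selection by univariate association, then by minimum p within a gene. Assumed, because the plan does not say: 1, 3 or 5 SNPs per gene; within-gene linkage disequilibrium of 0.6; allele frequencies 0.15 to 0.5; entry at p < .05 (.01 and .10 as alternatives); stage 2 on end-of-treatment main effects.

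**3. Why the direction is certain.** In a simple regression a SNP enters only if its sample r² = t²/(t² + N - 2) passes the critical value. At N = 50 and p < .05, t = 2.011, so r² must be at least 4.04/52.04 = 0.078. At p < .01, t = 2.682 and the floor is 7.19/55.19 = 0.130. A SNP with no effect can enter only by showing at least that much explained variance. With independent SNPs the chance that at least one enters is 1 - 0.95^m: 34%, 71% and 87% for m = 8, 24 and 40.

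**4. Size with no true effect, N = 50, entry at p < .05** (simulation of the two-stage rule):

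| SNPs per gene | 1 | 3 | 5 |
|---|---|---|---|
| A genetic model arises | 34% | 67% | 85% |
| In-sample R² when it arises | 0.127 | 0.165 | 0.200 |
| In-sample R², all data sets | 0.043 | 0.111 | 0.169 |
| Ten-fold cross-validated R², all data sets | -0.048 | -0.120 | -0.176 |

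The last two rows are the like-for-like comparison. The third row is about the product of the first two, for example 0.674 × 0.165 = 0.111. Cross-validated R² is 1 minus the ratio of squared prediction error to that of a model with arm only, with screening repeated in each fold.

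**5. Sensitivity, no true effect.**

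- Entry at .01: a model arises in 8.5/21.3/31.3% of data sets with R² 0.168/0.176/0.178, so the average over all data sets is about 0.01/0.04/0.06.
- Entry at .10: 56.6/92.3/98.1% with R² 0.122/0.180/0.237, an average of about 0.07/0.17/0.23.
- N = 35, entry at .05: R² when a model arises is 0.182/0.222/0.268.
- Adjusted R² does not cure the bias. In a separate run with independent SNPs and N = 50, mean R² was 0.04/0.12/0.18 and mean adjusted R² 0.04/0.10/0.15.
- Not simulated: stage-2 selection on interactions or on follow-up outcomes, and haplotype tests. More ways to enter would raise these figures; stronger linkage disequilibrium would tend to lower them.

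**6. With one true SNP** (empty models counted as 0; the fitted model applied to 4,000 new patients):

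| True share | In-sample | In new patients | Cross-validated |
|---|---|---|---|
| 10% | 0.129/0.189/0.231 | 0.012/-0.042/-0.085 | -0.006/-0.054/-0.114 |
| 20% | 0.227/0.274/0.310 | 0.138/0.094/0.053 | 0.113/0.079/0.019 |

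Cross-validation is about 0.01 to 0.03 below the new-patient value.

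**7. Does anything in the plan correct this?** The short gene list reduces the number of tests but does not change how a selected variant is scored. The permutation gives a significance level for one stage-1 haplotype test. The DNA added under Optional Genetics Component comes from a medication-discontinuation study and a longitudinal study. No outcome after exposure therapy with DCS or placebo is described for either, so they supply no validation set.

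**The case against.** **It is exploratory.** Section 1 calls this an initial study and leaves a wider search to larger samples; the Optional Genetics Component text concedes that genetic samples are few. Nowhere does the plan promise a validated R-squared, so a plain label would remove most of the harm. This stands and is why the point is minor. It is not a complete answer, because section 2 also describes the approach as hypothesis-driven.

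**Cross-validation answers a different question.** If the target is the variance that the true SNPs explain, the in-sample figure is the nearer one. For a 20% SNP its error is +0.03/+0.07/+0.11, against -0.09/-0.12/-0.18 for cross-validation; for a 10% SNP, +0.03/+0.09/+0.13 against -0.11/-0.15/-0.21. This stands. Cross-validated R-squared estimates how the fitted model predicts in new patients. The section 2 hypothesis speaks of prediction, which supports that target, but the choice must be stated.

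**The cross-validated figure is unstable.** With a true 20% SNP it was negative in about 17/28/41% of simulated data sets. When no SNP enters stage 2 under the null it still averaged about -0.05/-0.15/-0.22, because single folds select SNPs. Both stand and belong in the plan's wording.

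**Conclusion.** The point holds, at minor severity. The upward bias follows from the procedure and needs no assumed input. Its size does: at N = 50 with no true effect, the average in-sample R-squared runs from about 0.01 (one SNP per gene, entry at .01) to about 0.23 (five SNPs, entry at .10), with 0.04/0.11/0.17 at entry .05. That validation is missing is a reading of what the text leaves out. That N may fall below 50 follows from optional consent and the possible ancestry restriction.

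Three stronger readings are tempting and not supported.

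- **That a spurious genetic model will usually appear.** The chance runs from about 9% to 98% across the settings tried, and the documents fix neither the threshold nor the SNP count.
- **That the bias reaches the primary result or the design of the next trial.** The DCS comparison does not use this model. The Power analysis paragraph ties future design to between-group effect sizes and says nothing of a genetic R-squared.
- **That a search-wide multiplicity adjustment of stage 1 is also required.** That is a separate trade-off. Over 8 genes × 1/3/5 SNPs × 2 tests × 3 time points = 48/144/240 tests, power for a SNP explaining 10% of variance would fall from 64% to 16/9/7%.

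**What to change.** In section 6, Genetic Analyses:

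1. Fix the stage-2 entry threshold and outcome time point in advance.
2. Label the in-sample R-squared as apparent and exploratory.
3. Report beside it a cross-validated R-squared, for example repeated ten-fold, with SNP screening and minimum-p selection redone inside every fold. Express it as the increment over arm and the clinical predictors.
4. State that this figure estimates how well the fitted model predicts in new patients, not the variance explained by the true SNPs.
5. State in advance what is reported when no SNP enters stage 2.

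The cost is wording and computing time. The price in reporting is a smaller and imprecise figure: its standard deviation across data sets is 0.07/0.11/0.14 with no effect and 0.14/0.17/0.19 with a 20% SNP, and it will sometimes be negative when a real effect exists. That imprecision should be stated alongside the result. Bootstrap optimism correction is an alternative, but it over-corrected under the null with 1 or 3 SNPs per gene (-0.098 and -0.170, against -0.048 and -0.108 in new patients).
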